5.1.1.2 Prophylaxis initiation cohort for evaluation

[figure not shown]
Patients will be eligible to enter the cohort on initiation of Takhzyro, Haegarda, or Cinryze as a prophylactic treatment during October 10, 2008 through October 3rd, 2019 (Figure 1). October 2008 was selected as the start of the study period based on the approval date for Cinryze, the earliest of the medications to be approved. Clinical experts confirmed that 2008 reflects the current treatment paradigm of medications targeting the BK pathway and that all new treatments after 2008 reflect a continual shift away from inferior anabolic androgen therapies. The study period was also selected to maximize sample size for this rare disease.

New use will be defined as no use of Takhzyro or Haegarda, during the 180 days prior (washout period), and no use of Cinryze as a prophylactic treatment during this 180-day washout period. Because Cinryze is used for both acute attacks (off label) and prophylaxis, patients will be excluded based on evidence of prophylactic use of Cinryze (see definition in Annex 2) during the 180 days prior to cohort entry and will be required to have continuous enrollment and evidence of recurring use during the 90 days following cohort entry. Patients receiving other prophylactic treatments (see Annex 1) during the baseline period will also be excluded. Each patient will be included only once, on the first qualifying event. Patients will be required to have at least 180 days of enrollment prior to cohort entry to obtain baseline attack rates.

Using this cohort, we will evaluate baseline outcomes. Patients' demographic characteristics will be assessed at cohort entry. Patients' attack rates, and attack-related medical service utilization and costs will be evaluated.

Note: HAE does not have specific ICD9/10 diagnostic codes. We used initiation of HAE specific treatment to identify patients of interest (i.e., patients with HAE). The method of using HAE treatments to identify HAE patients has been used widely in the literature (Tachdjian 2020, Banerji 2020, [Vande Walle 2018](#)).¹⁻³ In addition, there is no indication that HAE treatments are used off-label for non-HAE patients.

Figure 1: Prophylaxis initiation cohort study design diagram

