Annex 1: HAE drugs

Generic	Brand (Administration)	Acute Attack Dose	Long-Term Prophylaxis Dose	How Supplied
C1 Inhibitor, Human (plasma derived C1 inhibitor [pdC1INH])	Cinryze* (IV)	Adults† 1,000 units once. Additional 1,000 units IV if no improvement 60 minutes after first dose. (not studied in children)	Adults & Children ≥12 years 1,000 units every 3-4 days Max Dose: 2,500 units or 100 units/kg every 3 days Children (6-11 years) 500 units every 3-4 days Max Dose: 1,000 units every 3 days Short-Term Prophylaxis† (before a procedure) 20 units/kg or 1,000 units immediately prior to procedure	Cinryze 500 units Powder Vial Reconstitute with 5mL SWFI Concentration: 100 units/mL
	Haegarda* (SC)		Adults & Children ≥6 years 60 IU/kg twice weekly (every 3-4 days)	Haegarda 2000 IU Powder Vial Reconstitute with 4mL SWFI Concentration: 500 IU/mL Haegarda 3000 IU Powder Vial Reconstitute with 6mL SWFI Concentration: 500 IU/mL
	Berinert* (IV)	Adults & Children ≥6 year 20 IU/kg once		Berinert 500 IU Power Vial Reconstitute with 10mL SWFI Concentration: 50 IU/mL

Generic	Brand (Administration)	Acute Attack Dose	Long-Term Prophylaxis Dose	How Supplied
Lanadelumab	Takhzyro* (SC)		Adults & Children ≥12 years 300mg every 2 weeks. After 6 months, reduce to every 4-week dosing if patient well-controlled.	Takhzyro 300mg/2mL Solution Vial Concentration: 150mg/mL
C1 Esterase Inhibitor, Recombinant (recombinant human C1 inhibitor [rhC1INH])	Ruconest* (IV)	Adults & Children ≥13 years (non-laryngeal attacks) 50 IU/kg/dose Max Dose: 4,200 IU/dose; 8400 IU per 24 hours	Adults & Children ≥13 years† 50 IU/kg/dose once or twice weekly Max Dose: 4,200 IU/dose once or twice weekly Short-Term Prophylaxis† (before a procedure) 50 IU/kg or 1,000 units immediately prior to procedure	Ruconest 2100 IU Powder Vial Reconstitute with 14mL SWFI Concentration: 150 IU/mL
Ecallantide	Kalbitor* (SC)	Adults & Children ≥12 years 30mg once (administered as three injections of 10mg) Max Dose: 60mg in 24 hours		Kalbitor 10mg/mL Vial Solution for Injection (3 vials per package)
Icatibant	Firazyr (SC)	Adults 30mg once. Repeat administrations in 6-hour intervals. Max Dose: 90mg in 24 hours (EU Pediatric Dosing Weight Based)		Firazyr 30mg/3mL Solution Vial Icatibant 30mg/3mL Solution Prefilled Syringe
Berotrastat	Orladeyo* (Oral)		Adults & Children ≥12 years 150 mg once daily. Adjustment: 110mg once daily for hepatic impairment or GI reactions.	Orladeyo 110mg Capsule Orladeyo 150mg Capsule

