Android Methitest Testred Virilon (Methyltestosterone)	NDCs: 00187-0902-01 00115-1408-01 00187-0901-01 00115-7037-01	Clinical Pharmacology Database²⁰
Winstrol (Stanozolol)	NDCs: 0024-2253-04??	Clinical Pharmacology Database²⁰
Prophylactic use of Cinryze and Ruconest	Algorithm and code lists	Source
Cinryze prophylactic use	Cinryze is indicated for prophylaxis, but is used off-label for acute attacks. Prophylactic use will be defined as continuous refills of Cinryze averaging ≥ 1500 IU/week for ≥ 90 days.	Riedl 2018²²
Ruconest prophylactic use	Ruconest is indicated for on-demand use, but is used off-label for prophylaxis. Patients with Ruconest prophylactic use will be excluded from the cohort. Prophylaxis use will be defined as continuous refills of Ruconest averaging 50 IU/kg once weekly for 90 days.	Riedl 2018²²
every four-week	Used to determine if a dose reduction occurred.	

administration of Takhzyro	This will be measured over a 90-day follow-up period based on total dose <= 1200 mg over that period. The 1200 mg is based on three 300 mg injections plus one additional injection to account for potential variation in exact timing.	
Attack severity	Algorithm and code lists	Source
Severe	
ED visit with/without hospitalization, identified based on “Type of service” coded as inpatient or emergency room. Events identified as HAE-specific include at least one of the following diagnose (as a primary diagnosis for hospitalizations /or treatments indicative of an attack:
 
 € Codes often associated with HAE: ICD-9-CM 277.6 or ICD-10-CM D84.1 € Angioedema diagnosis: ICD-9-CM 995.1 or ICD-10-CM T78.3* € Administration of on-demand HAE treatment € Diagnosis of swelling, abdominal pain, or asphyxiation: 
 o ICD-9-CM 518.81, 518.84, 787.0*, 782.2, 789.0*, 786.02, 786.05, 786.1 o ICD-10-CM J96.0*, J96.2*, J96.9*, R06.0*, R06.1, R10.*, R11.*, R22.0*, R22.1, R19.0 	
UpToDate states severe attacks are treated in ED.²³
 
Tachdjian 2020¹
 
Zilberberg 2010²⁴
 
Longhurst & Bork, 2019

Non- severe attack	
Each dose of an on-demand therapy over two acute attack doses is considered an attack. The number of doses dispensed will be calculated from the quantity dispensed and recommended dose and
 
Any on-demand therapy administered outside an inpatient or emergency room setting will be considered a non-severe attack.
	
Utilization	Algorithm and code lists	Source

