Annex 3: Results Table Shells

Table 1: Baseline characteristics of patients with HAE

Characteristic	RWE results	Notes	Prior ICER review base case	Prior ICER review source
Mean age			39.63	Banerji et al. 2017, ³⁰ Longhurst et al. 2017, ³¹ Zuraw et al. 2010 ³²
Female, %			68.4%	Banerji et al. 2017, ³⁰ Longhurst et al. 2017, ³¹ Zuraw et al. 2010 ³²
Mean weight, females			76.4	Fryar et al. 2016 ³³
Mean weight, males			88.8	Fryar et al. 2016 ³³
List of top 10 non-HAE therapies (therapeutic class)				

Table 2: Attack rates, utilization, and costs in the six-month baseline period before initiation of prophylaxis treatment

Characteristic	RWE results	Notes	Prior ICER review base case	Prior ICER review source
ATTACK RATES AND TREATMENTS ADMINISTERED				
Mean attack rate per month (HAE-specific severe and non-severe)			3.39	Banerji et al. 2017, ³⁰ Longhurst et al. 2017, ³¹ Zuraw et al. 2010 ³²
Number of patients who are attack free in baseline period before starting prophylaxis therapy		Due to drug indications and health plan requirements, this is expected to be minimal or 0.	-	

Distribution of severe attack free months			-	
Proportion of attacks, by severity				
Severe - HAE specific			-	
Severe - All-cause			-	
Non-severe			-	
Treatment administered – Non-severe attacks				
Self			64.9%	Riedl et al, 2015 ³⁴
Home nurse			13.8%	Riedl et al, 2015 ³⁴
Outpatient			21.3%	Riedl et al, 2015 ³⁴
% of severe-HAE specific attacks resulting in hospitalization			40.9%	Zilberberg et al 2011a ³⁵
% of hospitalized patients receiving cricothyrotomy/tracheotomy			40.0%	Bork et al ³⁶
% of cricothyrotomy/tracheotomy patients who receive artificial respiration			40.0%	Bork et al ³⁶
% of hospitalized patients who are intubated			60.0%	Bork et al ³⁶
% of intubated who receive artificial respiration			26.7%	Bork et al ³⁶
% of attacks treated with these on-demand drugs				Assumption in model
Berinert			25%	
Kalbitor			25%	

Firazyr			25%	
Ruconest			25%	
BASELINE HAE-SPECIFIC COST OUTCOMES				
Costs per home nurse			\$179	Graham et al 2017 ³⁷
Costs per physician office visit			\$266	Graham et al 2017 ³⁷
Costs per ED visit			\$1,796	Zilberberg et al 2011a and 2011b ^{35,38}
Costs per hospitalization			\$5,782	Zilberberg et al 2011a and 2011b ^{35,38}
BASELINE HAE-SPECIFIC UTILIZATION OUTCOMES				
Average number of home visits			-	
Average number physician office visits			-	
Average number of ED visits			-	
Average number of hospitalizations			-	

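### The Ruconest exclusion rule can also catch on-demand users who treat about one attack a week, so entry to the baseline cohort partly depends on the dispensings that form the primary attack rate and drug mix; the net direction of the error is not established.

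*Protocol*

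**What the plan says.** Section 5.1.1.2 of the protocol sets the exclusion for the baseline cohort: "Patients receiving other prophylactic treatments (see Annex 1) during the baseline period will also be excluded". For Ruconest, Annex 2 first notes the drug's two roles, "Ruconest is indicated for on-demand use, but is used off-label for prophylaxis", then states the consequence, "Patients with Ruconest prophylactic use will be excluded from the cohort", and the test: "Prophylaxis use will be defined as continuous refills of Ruconest averaging 50 IU/kg once weekly for 90 days".

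Annex 1 gives the acute-attack dose as "50 IU/kg/dose Max Dose: 4,200 IU/dose; 8400 IU per 24 hours" and the off-label long-term prophylaxis dose as "50 IU/kg/dose once or twice weekly Max Dose: 4,200 IU/dose once or twice weekly". The amount per dose is the same in both columns.

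Under section 5.2.1.4 and Annex 2, every on-demand dose beyond two held in reserve counts as a non-severe attack. Section 5.4.1.1 divides attacks by person-months over the six months before initiation. Table 2 in Annex 3 reports this as "Mean attack rate per month (HAE-specific severe and non-severe"), next to a prior base case of 3.39, and also reports the share of attacks treated with each of four on-demand drugs. The two sensitivity analyses named in section 5.4.1.4 vary the five-day window and the two on-hand doses. Neither they nor the limitations in section 5.4.1.5 mention the Ruconest exclusion.

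**The concern.** The rule is meant to separate prophylaxis from acute treatment, but its threshold is one acute dose a week. The only other condition is that refills be continuous, which the protocol does not define. It uses no diagnosis, visit record or regularity of interval. A patient with frequent attacks who treats each one on demand can therefore look like a weekly prophylaxis user.

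This matters because the exclusion and the outcome draw on the same dispensings in the same six months. On-demand patients removed in error have high attack rates, and the attacks lost with them are Ruconest-treated. Attack rate and on-demand drug mix are both questions under the primary objective and are intended to update the cost-effectiveness model. Section 4 of the protocol itself warns that small changes in attack frequency could alter the cost-effectiveness results substantially.

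**Working it through.** The plan states no figure for the effect of this rule, so there is none to reproduce.

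**Inputs from the protocol.** Threshold of 50 IU/kg a week over 90 days (Annex 2). Acute dose 50 IU/kg, cap 4,200 IU per dose, maximum 8,400 IU in 24 hours, vial 2,100 IU (Annex 1). Base-case rate 3.39 a month and mean weights 76.4 and 88.8, taken as kg (Annex 3). A month is 365.25/12 = 30.44 days.

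**Step 1: attack frequency that meets the rule.**
- At one dose per attack: one attack a week, or 30.44/7 = 4.35 a month. Over 90 days, 90/7 = 12.9, so 13 doses.
- In whole vials at 76.4 kg: the threshold is 50 × 76.4 = 3,820 IU a week and two vials give 4,200 IU. So 3,820/4,200 = 0.91 attacks a week, or 3.95 a month.
- At 88.8 kg: the threshold is 4,440 IU and the dose is capped at 4,200 IU. So 4,440/4,200 = 1.06 attacks a week, or 4.60 a month.
- If every attack took two doses: 4.35/2 = 2.17 a month. This is an extreme case, because 8,400 IU is a maximum and not stated as usual practice.

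**Step 2: where this lies on the outcome scale.** By the protocol's own count, one dose a week for 180 days gives 180/7 = 25.7 doses. Then (25.7 − 2)/6 = 3.95 attacks a month, above the 3.39 base case.

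**Step 3: chance that a purely on-demand Ruconest user meets the rule.** Assume a mean of 3.39 attacks a month, one dose per attack, and a refill condition that spares no one. The mean over 90 days is 3.39 × 90/30.44 = 10.0. The probability of 13 or more is:

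| Variation between patients (assumed) | P(≥13 in a fixed 90 days) |
|---|---|
| None (Poisson) | 21% |
| Gamma shape 4 | 29% |
| Gamma shape 2 | 30% |
| Gamma shape 1 | 29% |

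In this fixed window, those excluded average 4.2-7.6 attacks a month and those kept 1.7-3.2.

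**Step 4: effect on the cohort rate.** The rule does not say which 90 days of the baseline count. The simulation (400,000 patients) therefore tried three readings: the last 90 days, either 90-day half, and 26 or more doses over all 180 days. With s the share of patients who treat only with Ruconest, e the fraction of them excluded and r the rate in those kept:

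rate = [(1 − s) × 3.39 + s(1 − e) × r] / [(1 − s) + s(1 − e)]

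| s (assumed) | Cohort rate a month | Change from 3.39 |
|---|---|---|
| 5% | 3.33-3.38 | about −0.2% to −2% |
| 10% | 3.26-3.37 | about −0.5% to −4% |
| 25% | 3.04-3.35 | about −1% to −10% |

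The lowest value arises with s = 0.25, e = 0.345, r = 1.46: (2.5425 + 0.2391)/(0.75 + 0.1638) = 3.04.

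**Step 5: effect on drug mix at s = 25%.** The Ruconest share of attacks is s(1 − e)r / [(1 − s) × 3.39 + s(1 − e)r].
- Strongest case (e = 0.345, r = 1.46): 0.239/2.782 = 9%.
- Mildest case (e = 0.114, r = 3.22): 0.713/3.256 = 22%.

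Without the exclusion the share would be 25%. The drug mix therefore moves proportionally more than the rate.

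**Step 6: errors in the other direction.** Under the 4,200 IU cap, a once-weekly prophylaxis user above 4,200/50 = 84 kg averages less than 50 IU/kg. At 88.8 kg the average is 4,200/88.8 = 47.3. Prophylaxis courses shorter than 90 days also do not qualify. Such patients can stay in the cohort, and each of their doses beyond two is then counted as an attack: about 3.95 spurious attacks a month for a full six months of weekly use.

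**The case against.** The strongest reply is that the rule is not based on volume alone. Continuous refills may spare patients who refill irregularly after attacks, and the definition is taken from a cited treatment-pattern study that cannot be examined here. This stands as far as size goes: the 21-30% assumes the condition spares no one, so it is nearer a worst case than an estimate. It does not remove the problem, because the condition is undefined and a patient with regular weekly attacks would still meet it.

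A reader might infer that the baseline attack rate is biased down. The documents do not support that. Some exclusion is needed, since a retained prophylaxis user contributes spurious attacks, and the missed users in step 6 push the rate up. Only the effect of wrongly excluding on-demand users has a known sign.

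The 25% Ruconest figure is one of four equal model assumptions about attacks, not an observed share of patients. At a 5% share the effect on the rate is at most about 2%. This objection also stands, and is why a range of shares is shown.

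Finally, section 5.4.1.5 concedes that no validated claims algorithm for attack rates exists and refers to a separate model analysis plan for how the estimates are used. The list in section 5.4.1.4 is also open-ended, and further runs could sit in an analysis plan. That lowers the weight of the point. But the exclusion rule is fixed in this protocol, and its general caveat about measuring attacks does not cover selecting patients on those same dispensings.

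**Conclusion.** The point holds in limited form. Because one acute dose and one weekly prophylactic dose of Ruconest are the same amount, the Annex 2 rule can exclude on-demand users with about one attack a week, and it does so on data that also form the primary outcome.

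In isolation, that error would lower the rate by about 0.2-2% if Ruconest-only users are 5% of patients and by about 1-10% if they are 25%. It would lower the Ruconest share of attacks by more. These figures rest on 3.39 attacks a month in all patients, one dose per attack, the assumed spread between patients, and a refill condition that spares no one. The real Ruconest share is unknown. The net direction, once missed prophylaxis users are counted, is not established. This is worth a cheap addition to the plan and is no reason to drop the exclusion.

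**What to change.** Keep the exclusion for the main cohort. Then:

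1. Report the number of patients excluded only by the Ruconest rule.
2. Add to section 5.4.1.4 a run of the attack rate, severity split and on-demand drug mix that keeps those patients and counts their Ruconest as on-demand treatment.
3. Present the two results as a sensitivity range for the model input. They should not be labelled lower and upper bounds, because the main cohort may still contain missed prophylaxis users.

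The cost is one extra cohort run and a sensitivity row in Table 2. The downside is that true Ruconest prophylaxis users add spurious attacks in the added run, which the text beside it should say. If the count of excluded patients is very small, it will itself show that the issue is negligible.

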5.2.1.1 Patient characteristics

The following patient characteristics will be evaluated on each patient's cohort entry date:

- Age
- Sex
- Weight

For the entire cohort, a list of the top 10 non-HAE therapies used over the baseline period will also be evaluated. We will evaluate the most used therapeutic classes across all patients. In clinical practice, patients may be on additional therapies for comorbidities. Some of these therapies (e.g., estrogens) may be associated with increased risk of HAE attacks.⁴ We will provide descriptive information on the most common therapies outside of HAE treatment for patients within the cohort.

Note: weight values may be limited in the Clinformatics® Data Mart. If needed, we will create an additional HAE patient cohort in Optum's De-identified Integrated Claims-Clinical dataset, which combines adjudicated claims data with Optum's Electronic Health Record data, to obtain a larger sample of HAE patients with weight values.

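### Annex 2's Ruconest prophylaxis exclusion omits Annex 1's 4,200 IU per-dose maximum and needs an individual weight, so some prophylaxis users can stay in the cohort and have their doses counted as attacks

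*Protocol*

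**What the plan says.** Section 5.1.1.2 of the protocol sets a general exclusion: "Patients receiving other prophylactic treatments (see Annex 1) during the baseline period will also be excluded". Ruconest needs an algorithm because it serves both as on-demand treatment and, off label, as prophylaxis. Annex 2 provides it: "Patients with Ruconest prophylactic use will be excluded from the cohort", followed by "Prophylaxis use will be defined as continuous refills of Ruconest averaging 50 IU/kg once weekly for 90 days". The rule states no comparison sign, no tolerance and no upper limit on the dose.

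Annex 1 gives the long-term prophylaxis schedule for Ruconest as "50 IU/kg/dose once or twice weekly Max Dose: 4,200 IU/dose once or twice weekly", and the supply form as "Ruconest 2100 IU Powder Vial". Its acute-attack entry has the same 50 IU/kg per dose and the same 4,200 IU per-dose maximum.

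On weight, Section 5.2.1.1 notes that "weight values may be limited in the Clinformatics® Data Mart" and proposes, if needed, an additional cohort in a linked claims and health-record dataset.

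Section 5.2.1.4 and Annex 2 count each dispensed on-demand dose beyond two as a non-severe attack. Section 5.4.1.1 puts these attacks into the primary baseline rate.

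**The concern.** The two annexes describe the same use with different arithmetic. Annex 2 asks for a weekly average proportional to body weight without limit, whereas Annex 1 stops the dose at 4,200 IU. Above the weight where the maximum starts to bind, a patient who follows the Annex 1 once-weekly schedule exactly falls short of the Annex 2 average. The exclusion then fails for patients it was written to catch. It fails in a different way for anyone without a recorded weight, because IU/kg cannot be computed.

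A missed prophylaxis user is not a neutral addition. Acute and prophylactic doses are the same size in Annex 1, so the dispensing data turn each prophylactic dose after the second into one apparent non-severe attack. The error runs upward in the primary baseline attack rate and in Ruconest's share of on-demand treatment in Annex 3, Table 2. Section 4 itself says that small changes in attack frequency can alter the cost-effectiveness result substantially.

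**Working it through.** **Inputs.** Annex 2: 50 IU/kg per week over 90 days. Annex 1: 50 IU/kg per dose, maximum 4,200 IU per dose, once or twice weekly; vial 2,100 IU. Annex 3, Table 1: mean weights from the prior review, 76.4 for females and 88.8 in the row "Mean weight, males" (no unit printed; taken as kg). Section 5.1.1.2: 180-day baseline. The plan states no figure of its own to reproduce here.

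**Weight at which the maximum binds.**
- Once weekly: 4,200 / 50 = 84 kg.
- Twice weekly: 2 × 4,200 / 50 = 168 kg.

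**Once-weekly user, fully supplied, rule read as a minimum.** Required = 50 × weight; scheduled = the lower of 50 × weight and 4,200.

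| Weight (kg) | Required IU/week | Scheduled IU/week | IU/kg | Rule met? |
|---|---|---|---|---|
| 76.4 | 3,820 | 3,820 | 50.0 | yes |
| 84 | 4,200 | 4,200 | 50.0 | yes |
| 88.8 | 4,440 | 4,200 | 47.3 | no |
| 100 | 5,000 | 4,200 | 42.0 | no |
| 120 | 6,000 | 4,200 | 35.0 | no |

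In whole vials, the 76.4 kg patient receives 2 × 2,100 = 4,200 IU, or 55.0 IU/kg, so there is some slack below 84 kg and none above it.

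**The neighbouring rule.** Cinryze prophylaxis in Annex 2 is at least 1,500 IU/week for at least 90 days, with no weight needed. Annex 1 gives 1,000 units every 3-4 days, which is 1,000 × 7/4 = 1,750 to 1,000 × 7/3 = 2,333 per week. The Cinryze threshold is therefore 1,500/2,333 = 64% to 1,500/1,750 = 86% of schedule. Above 84 kg the Ruconest rule asks for more than 100% of the once-weekly maximum.

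**Effect for one missed patient**, with six baseline months in the denominator:
- Weekly for 180 days: 180/7 = 25.7 doses; 25.7 − 2 = 23.7; 23.7/6 = 3.95 apparent attacks per month.
- Weekly for 90 days: 90/7 = 12.9 doses; 12.9 − 2 = 10.9; 10.9/6 = 1.8 per month.
- Full 180 days under the Section 5.4.1.4 sensitivity analysis without the two-dose subtraction: 25.7/6 = 4.29 per month.

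**Effect on the cohort mean** (assumptions: 1-5% of the cohort missed for all 180 days, otherwise with attack rates like the rest): 0.01 × 3.95 = 0.04 to 0.05 × 3.95 = 0.20 attacks per month.

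**The case against.** Section 5.1.1.2 points to Annex 1 for other prophylactic treatments, and the maximum stands there. A programmer sent to that table might read the Annex 2 dose as the capped one. This does not settle the matter. Annex 1 lists Ruconest for acute and prophylactic use at the same dose, so only the Annex 2 algorithm can separate the two, and that algorithm is uncapped.

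Handling of missing weight could also be left to an analysis plan, and the additional cohort in Section 5.2.1.1 is offered to describe weight, not to run this exclusion. Both points are fair. Still, the protocol has chosen a rule that needs an individual weight while doubting that weights are available, and a separate cohort cannot supply weights for the patients being screened.

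The strongest objection is that any Ruconest threshold trades one error for another. In claims, weekly prophylaxis looks the same as about 4.3 acute attacks per month treated on demand (25.7/6), and such patients are plausible candidates for prophylaxis. A lower threshold will exclude some of them and pull the rate down. That stands as a cost. For patients with a recorded weight, however, the plan already accepts this trade below 84 kg, and carrying the maximum into the rule only treats heavier patients alike. For patients with no weight the trade is new and needs to be shown in the results.

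**Conclusion.** The conflict between the annexes is real, and the 84 kg crossover is exact under the minimum reading. The rule misses fully supplied once-weekly users above 84 kg and cannot be applied where weight is absent. For missed users the bias in the baseline attack rate and in the Ruconest share is upward. Neither sensitivity analysis in Section 5.4.1.4 would reveal it. The size for the study is unknown: the number of Ruconest prophylaxis users is not given and may be small or zero, and the 0.04-0.20 per month rests on an assumed 1-5%.

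A reader might infer more than the documents support:
- *That most patients lack a weight.* Section 5.2.1.1 gives no share; it says only that values may be limited.
- *That twice-weekly users also escape.* Under the minimum reading, on which the 84 kg point itself depends, they qualify up to 168 kg. The absent comparison sign is a drafting gap to close; an exact-value reading is implausible, since whole vials alone give 55.0 IU/kg at 76.4 kg.
- *That 3.95 per month can be set against the prior base case of 3.39 in Annex 3, Table 2.* The first is one hypothetical patient with uninterrupted weekly supply; the second is a cohort mean.
- *That the biased rate passes straight into the model.* Section 5.4.1.5 refers to a separate model analysis plan for criteria on using attack estimates.

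**What to change.** Reconcile the Annex 2 classification rule with Annex 1:

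1. State Ruconest prophylactic use as continuous refills over at least 90 days with a weekly average of at least the lower of 50 IU/kg and 4,200 IU. A fully supplied once-weekly user then meets the definition at every weight.
2. For patients with no recorded weight, add a rule in dispensed IU per week, as the Cinryze rule already does, and fix its value before the data are examined. A flat 4,200 IU per week is one candidate, but it would miss once-weekly users of 42 kg or less, for whom 50 IU/kg is a single 2,100 IU vial.
3. Report the baseline attack rate with and without the patients excluded by the weight-free rule, and give their number.

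The cost is one amended definition, a recoded exclusion and one extra line of results. The downside is that some genuine frequent on-demand users, at about 4.3 doses per month or more, may be excluded; for those without a weight, the paired report shows how much this matters. The change concerns only the classification of claims and takes no position on dosing.

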5.1.1.4 Dose reduction cohort evaluating the exploratory research objective

[figure not shown]
The dose reduction exploratory cohort will only focus on patients initiating Takhzyro.

Patients will be eligible to enter the cohort on initiation of Takhzyro, during August 23, 2018 through July 5, 2019 (Figure 2). August 23, 2018 was selected as the start of the study period based on the approval date for Takhzyro. New use will be defined as no use of Takhzyro, during the 180 days prior to initiation (washout period). Each patient will be included only once, on the first qualifying event. Patients will be required to be continuously enrolled in the 180 days prior to

initiation and for at least 270 days post cohort entry. The FDA label for Takhzyro, states that patients whose attacks are well-controlled for six months should reduce dosing to every four weeks, thus the cohort will require a minimum of six months follow up plus 90 days to establish the new dosing regimen. To be included in the cohort, patients will be required to have dosing, on average, every two weeks during the 180 days post cohort entry.

Using the dose reduction cohort, we will determine the percent of patients that receive the less frequent dosing regimen after six months attack free.

Figure 2: Takhzyro dose reduction study diagram

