Pharmacy – on-demand drug utilization (# of scripts and total dose)			-	

Table 3: Descriptive analysis during follow-up (post initiation of prophylaxis)

Characteristic	Takhzyro initiators	Haegarda initiators	Cinryze initiators*	Notes
Mean age at initiation				
Female, %				

Distribution of severe attack free months				
Mean attack rate per month – severe-HAE specific- follow up period				
Proportion of patients with PDC >80%				
Switching- % patients switching to Takhzyro	N/A			
Switching- % patients switching to Haegarda		N/A		
Switching- % patients switching to Cinryze			N/A	

*Cinryze patients were required to be adherent to therapy in the 90 days post initiation to determine that they were taking Cinryze prophylactically (versus on-demand use). Takhzyro and Haegarda patients were not required to demonstrate adherence in the 90 days post initiation.

Table 4: Exploratory dose reduction outcomes

Characteristic	Takhzyro initiators	Notes
Percent of Takhzyro patients attack free for 6-month period		
Percent patients on every 4-week dosing for 6 months		
Percent of patients that titrated down to every 2-week dosing		

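### The every-four-week Takhzyro rule in Annex 2 has no continued-use condition, so patients who stop or switch are counted as dose reductions in the exploratory Table 4

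*Protocol*

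**What the plan says.** Annex 2 has an entry for every-four-week administration of Takhzyro. Its purpose is "Used to determine if a dose reduction occurred", and its whole content is "This will be measured over a 90-day follow-up period based on total dose <= 1200 mg over that period". The limit is explained: "The 1200 mg is based on three 300 mg injections plus one additional injection to account for potential variation in exact timing".

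Protocol 5.1.1.4 applies this to a cohort of Takhzyro initiators. On treatment, it asks for "dosing, on average, every two weeks during the 180 days post cohort entry". On observation, it asks for continuous enrolment before "initiation and for at least 270 days post cohort entry", that is, six months plus 90 days to establish the new regimen. The stated output is "we will determine the percent of patients that receive the less frequent dosing regimen after six months attack free". The matching row of Table 4 in Annex 3 reads "Percent patients on every 4-week dosing for 6 months".

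The neighbouring Annex 2 rules for prophylactic Cinryze and Ruconest both require continuous refills at a stated average dose. The Takhzyro rule has no such condition.

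**The concern.** The rule is meant to identify patients who moved to a less frequent regimen, but it tests only whether little drug was dispensed. Stopping, switching to Haegarda or Cinryze, and lapsing all produce little drug. Nothing in 5.1.1.4 removes these patients. Enrolment to day 270 excludes those who leave the plan, not those who leave the drug. The attack-free condition refers to the first six months, so it does not exclude later stoppers either.

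Section 4 names the unknown as the share of patients who change to the less frequent dose and stay on it, and says less frequent dosing could affect incremental cost-effectiveness. A percentage that mixes dose reduction with discontinuation does not answer that. Table 4 has no row for stopping or switching, so a reader could not see the mixture.

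**Working it through.** **Inputs.** From the protocol: 300 mg per injection and the two regimens (Annex 1: "300mg every 2 weeks. After 6 months, reduce to every 4-week dosing if patient well-controlled"); the 1200 mg limit and 90-day length (Annex 2); the 180-day and 270-day requirements (5.1.1.4). Assumed: the window is the 90 days after day 180, numbered here 0 to 89. Fill sizes are also assumed, since the protocol gives none.

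**The plan's own figure.** (3 + 1) × 300 mg = 1200 mg. This reproduces.

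**Does the limit separate persistent users?** Count injections in 90 days over every possible start day.
- Every 28 days: 3 injections (900 mg) in 22 of 28 alignments, 4 (1200 mg) in 6 of 28.
- Every 14 days: 6 or 7 injections (1800 or 2100 mg).

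So the limit works for patients who stay on one regimen throughout the window.

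**Patients who stop or switch.**
- Before the window: 0 mg ≤ 1200 mg, always counted as reduced.
- Two-weekly, single-vial fills, stopping by window day 56: at most 56 / 14 = 4 injections, 4 × 300 = 1200 mg, always counted.
- Stopping at window day 60: counted in 10 of 14 alignments (71%). At day 70: 5 injections, 1500 mg, never counted.

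**Two-weekly patients who miss fills.**

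| Assumed fill | Missed | Counted as reduced |
|---|---|---|
| 1 vial / 14 days | 1 | 0 of 14 |
| 1 vial / 14 days | 2 | 8 of 14 (57%) |
| 1 vial / 14 days | 3 | 14 of 14 |
| 2 vials / 28 days | 1 | 22 of 28 (79%) |
| 2 vials / 30 days | 1 | 30 of 30 |

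Example: three two-vial fills less one leaves 2 × 2 × 300 = 1200 mg.

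**The opposite error.** Take a patient who truly changes to four-weekly dosing at window day 42. With injections on days 0, 14, 28, 42 and 70, the total is 5 × 300 = 1500 mg, and the patient is missed. Every alignment gives at least 5 injections for a change at day 42 or later. For a change at days 21 to 35, 7 or 8 of 14 alignments (50–57%) are captured.

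**Combined effect.** Let r be the true share reducing, m the fraction of those missed, and s the share who stop or switch early enough to be counted. Then observed = r(1 − m) + s. With r = 20% (assumed):
- m = 0, s = 5% to 20%: 25% to 40%.
- m = 0.25, s = 5%: 15% + 5% = 20%, no net bias.
- m = 0.5, s = 5%: 10% + 5% = 15%, net bias downward.

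The protocol supplies none of r, m or s.

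**Would a floor be enough?** No. With a 900 mg floor, a two-weekly single-vial user who stops at window day 42 to 56 has 900 to 1200 mg and still passes. A true four-weekly user filling two vials every 56 days has one fill (600 mg) in 22 of 56 alignments and would be wrongly excluded. Evidence of continued use is needed instead.

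**The case against.** The strongest reply has four parts.

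- **Status.** The cohort is exploratory, and 5.1.1.3 says the post-initiation exploratory analysis will not directly influence the cost-effectiveness model. This stands as a limit on importance: no primary result is touched. It does not make the rule measure what it names, and Section 4 still lists this proportion among the model's uncertainties.
- **Intent.** The variable is named for a regimen and anchored on three injections, so an analyst might sensibly exclude patients with no fills. The written rule does not say so, and that reading would still admit a two-weekly user who stops mid-window.
- **Visibility.** Table 3 reports switching and adherence for Takhzyro initiators. That is the follow-up cohort, which is selected differently, so it does not show how many of those counted in Table 4 had stopped or switched.
- **Level of detail.** Fill-gap logic is often left to an analysis plan. Here the protocol fixes the rule itself, so the gap belongs to the protocol.

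A reader might go further and infer that the reported percentage must be too high, or that it equals the true percentage plus everyone who lapsed. The documents support neither. Late true reducers are missed, those stopping after about window day 70 on single-vial fills are not counted, and one missed fill is enough only with roughly monthly two-vial fills. Nor do the documents trace a path from this percentage to an overstated cost offset.

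**Conclusion.** The concern holds in a bounded form. As written, the rule counts as dose reductions all patients who stop or switch before the window, and two-weekly users who stop by about day 56 of it (roughly day 235 after cohort entry). Whether missed fills add to this depends on fill size. Relative to the same rule with a continued-use condition, the omission can only raise the exploratory percentage. The net direction and the size of the error are not determinable from the documents; the 15% to 40% range around an assumed true 20% is illustration only.

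A related mismatch needs reconciling. Table 4 speaks of four-weekly dosing for 6 months, while the rule looks at 90 days and the cohort guarantees only 270 − 180 = 90 days after month six.

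**What to change.** Amend the Annex 2 definition and Table 4. This is classification of claims only and takes no view on dosing.

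1. Keep the 1200 mg upper limit and state which 90 days it covers.
2. Add evidence of Takhzyro use through the end of the window. One form is supply reaching the window end at one vial per 28 days, counted from the last fill. Do not accumulate it over all fills: four vials would give 4 × 28 = 112 days and pass a two-weekly user who stopped at day 56. Another is a later Takhzyro fill where follow-up allows; entrants on 5 July 2019 reach the end of data (31 March 2020) at day 270, so it cannot be required of everyone.
3. Require no fill of another long-term prophylactic in the window.
4. Do not require two consecutive fill intervals within 90 days. For a four-weekly user filling two vials, that needs 2 × 56 = 112 days.
5. Report two-weekly, four-weekly, discontinued, switched and unclassified as exclusive rows. Two-vial fillers whose last fill could fit either regimen belong in unclassified unless a later fill settles it.
6. Reconcile the 6-month wording of Table 4 with the 90-day window.

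The cost is one revised definition, a few table rows and some extra analysis of claims already held. The reported percentage may be lower, some irregular fillers will be unclassified, and patients who change late in the window will still not be captured as four-weekly.
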